9.3.2. Outcomes

When available, the following variables will be collected after initiation of Mysimba/Contrave (Post-Index Date). A draft listing of variables available in each country is included in Appendix 3 and will be included as final in the Statistical Analysis Plan (SAP).

Proprietary and Confidential:

This document cannot be used, distributed, or reproduced in any way without the prior written consent of Currax Pharmaceuticals LLC.

- 1. BMI, height, and weight prior to index date, the date of initiation of the medication(s) of interest, (obtained directly from data sources; BMI may be calculated if height and weight available). In the event that BMI and/or weight are not available through licensed access to the Scandinavian National Patient Registries, an attempt will be made to identify the obese population through diagnosis codes or procedures such as counseling for weight loss. It should be noted that this approach may identify a more obese and more motivated population than what would be identified on the basis of BMI. In addition, an approach may be implemented to predict BMI or apply published algorithms predicting BMI. Details will be laid out in the SAP.
- 2. Weight will be obtained if available 16-24 weeks post-index date to evaluate use inconsistent with labelled indication. BMI after index date will be obtained in the same timeframe, if available.
- 3. Relevant comorbidities (obtained via ICD-10 codes):
 - 1. Weight-related comorbidities (i.e., type 2 diabetes, dyslipidaemia, hypertension)
 - 2. Neuropsychiatric conditions (mania, bipolar disorder, major depressive disorder [MDD], anorexia nervosa, bulimia)
 - 3. Uncontrolled hypertension
 - 4. Moderate or severe renal impairment
 - 5. End-stage renal disease
 - 6. Seizure disorder
 - 7. Hepatic impairment (defined by Child-Pugh score category)
 - 8. Central nervous system tumour
- 4. Concomitant medication use, including: naltrexone, bupropion, CYP2B6 inhibitors, CYP2B6 inducers, CYP2B6 substrates, CYP2D6 substrates, drugs that lower seizure threshold, opioid or opiate agonist, or MAOI (obtained via ATC [outpatient, Nordic data] or NDC [US data])
- 5. Pregnancy status and breastfeeding status (obtained via ICD-10 codes)
- 6. AESIs (obtained via ICD-10 codes):
 - 1. Seizures

- 2. Suicidality (i.e., suicidal ideation, attempted suicide or completed suicide)
- 3. Neuropsychiatric events (i.e., mania or depression)
- 4. Hepatotoxicity
- 5. Severe hypersensitivity reaction

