- 6. Serotonin syndrome
- 7. Major adverse cardiovascular events (i.e., cardiovascular-related death, non-fatal myocardial infarction, or non-fatal stroke)

Deaths will also be described by treatment group, for those with vital status available.

- 7. Treatment discontinuation (assessed using ATC [outpatient, Nordic data] or NDC [US data])
- 8. Reason(s) for treatment discontinuation (obtained via ICD-10 codes in the 90 days prior to discontinuation)

All variables will be identified from the data sources via a pre-specified list of definitions (i.e., code lists; see Appendix 2). Occurrence of AESI based on diagnostic codes will be summarized for all patients, and for a subgroup of patients who do not adhere to conditions of the EU SmPC for the Scandinavian countries (adapted to local SmPC as needed) or to the FDA SmPC for the US. Such criteria include: not meeting appropriate criteria for the indication [obese (BMI \geq 30 kg/m²), or being overweight (BMI \geq 27 kg/m² to < 30 kg/m²) and having at least one weight-related co-morbidity (e.g., type 2 diabetes, controlled hypertension, or dyslipidemia) based on diagnostic codes. If BMI is not available, diagnostic and procedure codes for obesity and weight loss will be applied, recognizing that it will likely produce a more obese population than would be identified by BMI. Subgroup analyses will also be conducted to assess continuous treatment in patients with either renal or hepatic impairment.

Initiation of specific medications that could result with the occurrence of an event corresponding to an AESI (e.g., newly initiating anti-epileptic/seizure medication, newly initiating medications indicated for mania or depression) will also be tabulated. For hepatotoxicity, liver function tests can be used (when available) in addition to diagnostic codes.

For reason(s) patients who discontinue treatment (i.e., do not refill their prescription), events (potential AESIs and contraindications) and clinical status (magnitude of weight loss or gain)

Proprietary and Confidential:

occurring within the 90-day window prior to discontinuation will be summarized. It should be noted that weight may not be available in the Scandinavian registries.

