9.3.3. Covariates

When available, the following variables needed to conduct analysis for the primary and secondary research objectives will be collected. Variable availability from each country will be summarized in the SAP and is included in Appendix 3 in draft form.

Demographics and Baseline variables (Within 365 days before index date unless otherwise stated below; as depicted in Figure 1):

- 9. Patient demographics (age and sex on index date) (obtained directly from data source)
- 10. BMI, height, weight (most recent value on or before the index date) (obtained directly from data sources; BMI may be calculated if height and weight available)
- 11. Relevant comorbidities (obtained via ICD-10 codes), including:
 - 1. Weight-related comorbidities (i.e, type 2 diabetes, dyslipidaemia, hypertension)
 - 2. Neuropsychiatric conditions (mania, bipolar disorder, major depressive disorder [MDD], anorexia nervosa, bulimia)
 - 3. Uncontrolled hypertension, if possible
 - 4. Moderate or severe renal impairment
 - 5. End-stage renal disease
 - 6. Seizure disorder
 - 7. Hepatic impairment (defined by Child-Pugh score category, if available)
 - 8. Central nervous system tumour

- 12. History of, or current substance abuse/dependencies including acute opiate withdrawal (obtained via ICD-10 codes)
- 13. History of uncontrolled hypertension, seizures, bipolar disorder, MDD, anorexia nervosa, or bulimia (obtained via ICD-10 codes)
- 14. Prior medication use, including: naltrexone, bupropion, CYP2B6 inhibitors, CYP2B6 inducers, CYP2B6 substrates, CYP2D6 substrates, Monoamine oxidase inhibitors, Opioids, Opium alkaloids and derivatives and drugs that lower seizure threshold (obtained via ATC [Nordic data] or NDC [US data]) see Appendix 2 and 2A
- 15. Pregnancy status and breastfeeding status (obtained via ICD-10 codes)

All variables will be identified from the data sources outlined below using a pre-specified list of definitions per database (Appendix 3), to be defined in the SAP as final.

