9.4.1.1. Danish National Health Registries

The analysis of the Danish population will be conducted with The Danish National Health registries, which includes data on reimbursed prescription drugs, medical encounter data, and related patient demographic and clinical variables. The National Prescription Registry (NPR), records medicine according to Anatomical Therapeutic Chemical (ATC) classification codes and product codes/names will be used to identify exposure to Mysimba. The NPR includes individual-level data on prescriptions filled by Danish residents at community pharmacies since 1995. The NPR contains 46 variables that describe each prescription, the patient receiving the prescription, the drug dispensed, the prescribing healthcare provider, and the pharmacy dispensing the drug. Additional data will come from the Danish National Patient Registry of hospital encounters, which includes information on diagnoses, selected treatments, and surgical procedures, and occurrence (not results) of diagnostic procedures of residents. The patient registry also includes administrative data consisting of the region the patient's residence, the admitting hospital, any referring healthcare providers or hospitals, reason for going to the hospital, and timing of hospitalization or treatment.

Data can also be linked to the Danish Laboratory Research Database, enabling researchers to further determine diagnoses and conditions through laboratory results. Denmark also has other registries that capture deaths, socioeconomic status, education, income, and social benefit data. Residents are identified and linked to all Danish registries by the Civil Personal Register (CPR) number and demographic information can be obtained from the Danish Civil Registration System. Based on current and projected Mysimba prescription sales and lack of reimbursement for Mysimba in Denmark, we do not anticipate that this database will include > 750 new users

of Mysimba who would be eligible for inclusion in the study as of December 31, 2023. Feasibility counts will be obtained at the time of the first interim report. Analysis of the database will be conducted at the time of interim analyses or final analysis if a total of >750 patients are eligible for study inclusion.

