9.4.1.4. Swedish National Registries

The Swedish Statistical Database for Medicinal Products contains data on all prescription drugs dispensed by pharmacies in Sweden from 2006 – 2020. The registry includes medications and any accompanying consumable products (e.g., food for special nutrition for children under 16 years of age) dispensed to residents of the Kingdom. Included among the data is information on patient information (gender, age, location), product information such as ATC classification codes, pharmaceutical names, and quantity dispensed, when medications were prescribed, costs, and healthcare provider information of who prescribed the drug. These data will be linked with the Swedish Inpatient Registry (or Hospital Discharge Register), which provides data on physical and psychiatric inpatient and hospital-based outpatient care, along with patient related data (including age, sex, county of residence), hospital and department the patient visited, timing and duration of hospitalization and discharge, medical diagnoses, procedures, and psychiatric care.

Based on current and projected Mysimba prescription counts and the lack of reimbursement of Mysimba in Sweden, we anticipate that this database will include > 750 new users of Mysimba who would be eligible for inclusion in the study as of December 31, 2023. Actual counts will be available with the first interim report. Analysis of the database will be conducted for the final report if there are >750 eligible patients at the time of interim or final analyses.

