Appendix 3. Variable Availability by Country (final list to be confirmed in SAP)

LEGEND: "--" indicates that the information is not available

Partial = may be available for some patients

Limited = anticipated to be underreported

Yes = likely to be available if true for patient

Unlikely = available for some patients; may not be accurate

Calculated = assumptions can be used to derive a variable for this information

Variable	US	Denmark	Norway	Sweden	Finland
Mysimba prescription	Yes				
Date of Mysimba	Yes				
prescription					
Mysimba dispensing	Partial	Yes	Yes	Yes	Yes
Date of Mysimba	Partial	Yes	Yes	Yes	Yes
dispensing					
Mysimba dosage for each	Partial				
dispensing					
Initial titration scheme	Maybe				
Dosing of Mysimba during	Maybe				
titration					
Dose adjustment of	Partial				
Mysimba (e.g., for special					
population)					
Maintenance dose of	Maybe				
Mysimba					
Mysimba days' supply	Calculated	Calculated	Calculated	Calculated	Calculated
Date of	Partial	Yes	Yes	Yes	Yes
eligibility/enrolment					
available to identify					
continued					
engagement/recording of					
clinic visits					
Age	Yes	Yes	Yes	Yes	Yes
Sex	Yes	Yes	Yes	Yes	Yes
BMI	Partial				
Height	Partial				
Weight	Partial				
Diabetes	Yes	Yes	Yes	Yes	Yes
Dyslipidaemia	Yes	Yes	Yes	Yes	Yes

Proprietary and Confidential:

This document cannot be used, distributed, or reproduced in any way without the prior written consent of Currax Pharmaceuticals LLC.

Anorexia nervosa	Yes	Yes	Yes	Yes	Yes
Bulimia	Yes	Yes	Yes	Yes	Yes
Hypertension	Yes	Yes	Yes	Yes	Yes
Uncontrolled hypertension	Yes	Yes	Yes	Yes	Yes
Moderate or severe renal	Yes	Yes	Yes	Yes	Yes
impairment	1 68	1 68	1 68	1 68	1 68
End-stage renal disease	Yes	Yes	Yes	Yes	Yes
Seizure	Yes	Yes	Yes	Yes	Yes
Seizure disorder	Maybe	Unlikely	Unlikely	Unlikely	Unlikely
Hepatic impairment via	Maybe				
Child-Pugh score	Mayoc				
Hepatic impairment via diagnosis	Yes	Yes	Yes	Yes	Yes
Central nervous system	Yes	Yes	Yes	Yes	Yes
tumour					
Substance use/abuse	Limited	Limited	Limited	Limited	Limited
Acute opiate withdrawal	Limited				
Acute alcohol or	Limited				
benzodiazepine withdrawal					
Suicidality	Limited	Limited	Limited	Limited	Limited
Mania	Limited	Limited	Limited	Limited	Limited
Bipolar disorder	Limited	Limited	Limited	Limited	Limited
Major depressive disorder	Yes	Yes	Yes	Yes	Yes
Hepatotoxicity	Yes	Yes	Yes	Yes	Yes
Severe hypersensitivity reaction	Limited	Limited	Limited	Limited	Limited

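### Type 2 diabetes, dyslipidaemia and hypertension are defined by ICD-10 codes alone, yet the diagnosis sources described for Sweden (and for Denmark, if included) are hospital registers, so patients managed only in primary care are scored as not having them

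*Protocol*

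**What the plan says.** Section 9.3.3 (Covariates) lists the baseline variables with a default window: "Within 365 days before index date unless otherwise stated below". Item 11 then gives the source, "Relevant comorbidities (obtained via ICD-10 codes), including", and its first entry is "Weight-related comorbidities (i.e, type 2 diabetes, dyslipidaemia, hypertension". No other window is stated for that entry. Section 9.3.2 (Outcomes) uses the same source after index, "Relevant comorbidities (obtained via ICD-10 codes", and describes the comorbidity part of the indication criterion as "e.g., type 2 diabetes, controlled hypertension, or dyslipidemia) based on diagnostic codes".

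Appendix 2 matches this. Diabetes is E10-E11, dyslipidaemia E78 and hypertension I10-I16, and no ATC code is attached to any of the three.

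On sources, section 9.4.1.1 says for Denmark "Additional data will come from the Danish National Patient Registry of hospital encounters". Section 9.4.1.4 describes the Swedish register as one "which provides data on physical and psychiatric inpatient and hospital-based outpatient care". Neither section describes a primary-care diagnosis source. Both describe a national prescription register.

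Appendix 3 rates diabetes, dyslipidaemia and hypertension as Yes in all four Nordic countries, with the legend "Yes = likely to be available if true for patient".

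**The concern.** The three conditions are ones that a patient may have treated by dispensed medicines without a hospital contact in a given year. Under the stated rule, such a Swedish or Danish patient carries no code and is recorded as free of the condition. This is not treated as missing data: section 9.7.5 deals with missing values, but an absent code reads as absence of disease.

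Three results are exposed:

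- Baseline comorbidity, which is part of primary objective 1, is reported too low.
- Section 9.7.3.1 plans incidence rates of new-onset comorbidities after index. If a prevalent case is missed at baseline, the first hospital code during follow-up can be counted as a new event.
- The final report will interpret findings across the Nordic sources (sections 6 and 9.7.1). Some differences between countries may reflect what each register covers.

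The prescription data that could close the gap are already in the study but are not used for this purpose.

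**Working it through.** The point is a textual one, so the passages are set side by side first. The plan states no figure for this and there is none to reproduce.

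**Definition.** Sections 9.3.2 and 9.3.3 and the code list in Appendix 2 agree: ICD-10 codes, with a 365-day look-back at baseline. The prior-medication item in section 9.3.3 covers naltrexone, bupropion, the CYP2B6 and CYP2D6 groups, MAOIs, opioids and drugs that lower the seizure threshold. It names no glucose-lowering, lipid-modifying or antihypertensive class. Appendix 2 does carry ATC codes for some such drugs (atorvastatin, simvastatin, atenolol, dapagliflozin), but Appendix 2a lists drugs by their CYP2B6 or CYP2D6 role, not as markers of disease.

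**Diagnosis source by country.**
- Denmark (9.4.1.1): registry of hospital encounters.
- Sweden (9.4.1.4): inpatient and hospital-based outpatient care.
- Finland (9.4.1.2): register described as covering inpatient and outpatient care.
- Norway (9.4.1.3): linked patient registries, with no hospital restriction stated.

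The mismatch between rule and source is therefore shown for Denmark and Sweden only.

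**Internal tension.** Section 9.4.1 puts being obese, or overweight with a comorbidity, among the Nordic variables that limited coding may misclassify. It gives no direction and no remedy. Appendix 3 rates all three conditions Yes in the same countries.

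**Scale, for illustration only.** Let p be the true share of users with at least one weight-related comorbidity, and s the share of those with a hospital ICD-10 code in the window. The documents give neither, so both are assumptions. Then

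- reported prevalence = p × s
- share wrongly scored as having none = p × (1 − s)

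With p = 0.5, and counts at the protocol's two database sizes (750 and 3,000 patients):
- s = 0.8: reported 0.5 × 0.8 = 40%; missed 0.5 × 0.2 = 10%, or 75 of 750 and 300 of 3,000.
- s = 0.5: reported 25%; missed 25%, or 188 of 750 and 750 of 3,000.
- s = 0.2: reported 10%; missed 40%, or 300 of 750 and 1,200 of 3,000.

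Over p from 0.3 to 0.7 and s from 0.2 to 0.8, the missed share runs from 0.3 × 0.2 = 6 to 0.7 × 0.8 = 56 percentage points. At s = 1 it is zero. So wide a range shows how the error works, but does not estimate it.

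**The case against.** **The SAP will settle it.** Section 9.3.3 leaves final definitions per database to the SAP, and Appendix 3 is a draft. That is a fair point about detail. But the protocol already fixes a rule and a code list, and a SAP that follows them inherits the problem.

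**The limitation is disclosed.** Section 9.4.1 concedes possible misclassification, and section 9.9.1 notes that diagnoses outside a medical encounter may not be captured. This stands as disclosure. It does not say that the error runs towards under-reporting, offers no correction, and sits badly with the Yes ratings.

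**Other sources may fill the gap.** Section 9.4.1 mentions disease registries, section 9.4.1.1 an optional Danish laboratory linkage, and section 9.9.1 private-practice care in Nordic databases. None of these enters the definition of the three conditions.

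**The scope is narrow.** This stands. Section 9.4 calls Denmark only possible, and section 9.4.1.1 does not expect it to exceed 750 eligible users. Sweden is expected to exceed 750 (section 9.4.1.4), so the firm case is Sweden.

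**The compliance split may be untouched.** This also stands. A reader might infer that overweight patients with a treated comorbidity will be counted as off-label under primary objective 2. The documents do not establish that. The comorbidity matters there only for BMI 27 to <30 kg/m², and Appendix 3 shows BMI (as Partial) for the US alone. Section 9.3.2 substitutes obesity and weight-loss codes when BMI is absent, section 9.7.2 adapts the criteria, and section 9.7.5 bars imputed variables from the indication test. Predicted BMI is mentioned in section 9.3.2 only as a possibility.

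**Conclusion.** The point holds in a limited form. As written, the plan under-reports type 2 diabetes, dyslipidaemia and hypertension at baseline in Sweden, and in Denmark if it is included. It can also count a first hospital code for an already treated condition as new onset. Neither effect depends on BMI. Both rest on one assumption: that some users are managed only in primary care and have no coded hospital contact in the 365 days.

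Three stronger readings are not supported:

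- It is not true that everyone treated in primary care is missed; a patient who also has a coded hospital contact in the window is captured.
- The Nordic synthesis does not merely compare registers. Section 9.7.1 plans analyses by country followed by interpretation, and no pooled estimate is planned. Differences in register coverage may explain part of what is seen.
- The error cannot be called large. No prevalence or sensitivity is given, and any figure is an assumption.

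An effect on the compliant/non-compliant comparison is conditional on the overweight-plus-comorbidity test actually being applied in the Nordic data. The change is worth making because the data are already in the study and a primary objective is affected.

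**What to change.** - In sections 9.3.2 and 9.3.3 and Appendix 2, define each condition in the Nordic data as an ICD-10 code **or** dispensings, by ATC code, from a prespecified list of corresponding drugs (glucose-lowering, lipid-modifying, antihypertensive) in the baseline window. State the minimum number of dispensings. Leave out drugs with major other uses where possible.
- Report the ICD-only definition alongside as a sensitivity analysis.
- Use the same combined rule to exclude prevalent cases from the new-onset analyses in section 9.7.3.1.
- In Appendix 3, change the rating for diagnosis-only capture of the three conditions in Denmark and Sweden from Yes to Limited, which its legend reserves for variables expected to be underreported. This also brings it into line with section 9.4.1.

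The cost is additional ATC codes applied to prescription registers already in the study. There are two downsides. Drugs with other indications will produce some false positives, and the number cannot be judged from the documents; the comparison with the ICD-only version shows how much the results move. The Nordic definition will also differ from the US one unless it is mirrored there, which matters because section 9.4.1 intends analogous methods.

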9.4. Data Sources

Data sources for the study were determined based on the country-specific launch and uptake of Mysimba/Contrave and final assessment of database suitability for conducting this study. Given the need for at least 548 days of availability in the data after the index date of Mysimba first use, and now that the NB-451 study is underway, four European (Norway, Finland, Sweden, and possible Denmark) and one US data source are planned for inclusion in the interim and final study reports.

9.4.1. European Data Sources

The analysis based on the European data sources will complement an analogous methodological approach based on the data source derived from the US to inform the overall safety analysis.

After presentation of feasibility results to PRAC, the following data sources are proposed:

- 1. Denmark (Danish National Health Registries) Mysimba not reimbursed
- 2. Finland (Finnish National Registries) Mysimba reimbursed but restricted to morbidly obese
- 3. Norway (Norwegian Health Registries) Mysimba reimbursed but restricted to morbidly obese

4. Sweden (Swedish National Registries) - Mysimba not reimbursed

Currax has engaged a qualified vendor and research partner(s) who will apply for access to the licensed Nordic registry data, following Ethics Committee (EC) approval of the study protocol in each of the Nordic countries. Finalization of the protocol and particularly the SAP will necessitate consideration of specific data fields and variables that are available through this licensing process.

These national, population-based research registries capture population data, health data (including registries of hospital encounters, laboratory results (Denmark only), disease registries), death data, and socioeconomic data within each country. Records cover nearly all citizens and residents in each country throughout their time in the country. The registries have high accuracy and completeness and are maintained electronically (Laugersen et al., 2021). The registries have a strong scientific track record for accurately measuring exposure to prescription medications (Wettermark et al., 2013; Laugersen et al., 2021). Upon obtaining a separate permission, hospital records can be reviewed if necessary for the purposes of validation.

All citizens of these countries are represented in these national registries until death or emigration, providing virtually complete long-term follow-up. Identification of individuals by their unique personal identifier permits linkage to other national health databases (Laugersen et al., 2021). Thus, a large amount of specialized information from specific registries, such as hospitalization, prescription, heart disease, and death registries, can be linked for research (Schmidt 2015; Laugersen et al., 2021). The registries are highly complete and accurate due to the automation of their processes, as well as laws and other incentives motivating healthcare providers to collect and send the data electronically to their national databases (Gribsholt et al., 2019). The data from each country are expected to contain sufficient information to elucidate occurrence and determine levels of all variables, with the following exceptions which may be prone to misclassification due to limited coding in administrative and clinical data: obese or overweight with at least one comorbidity, neuropsychiatric conditions, history or current substance use or dependence, breastfeeding status, initial titration scheme and dose adjustments (expected to be unavailable since only one dose/pack type is available in the Nordic countries and no measure of titration scheme or adherence is included within the data), and reason(s) for medication discontinuation. Any country database with at least 750 patients with at least 365

days of data before the index Mysimba use and at least 548 days of availability in the data after the index date of Mysimba will be evaluated for whether there is sufficient required patient data to conduct this study. If there is sufficient data and uptake indicating that the database will reach more than 3,000 patients within the timespan of this drug utilisation and safety study, then it will be added to the data sources for evaluation. It should be noted that reimbursement varies in Scandinavia, with no reimbursement for Mysimba in Sweden and Denmark, and reimbursement in Norway and Finland restricted to morbidly obese patients who are at higher risk of cardiovascular and other events.

